Participants are randomized (1:1) to receive placebo or vortioxetine by the investigational pharmacy at the University of Chicago. The study blind will be maintained by over-encapsulation, making placebo and active treatments appear identical in size, weight, shape, and color. Dosage changes and reductions will not be permitted during the study and participants will be discontinued if they experienced intolerance.

Baseline Visit Assessments

Those subjects who appear appropriate for the study, based on telephone screening, will be invited for a baseline assessment. The duration of the baseline assessment will be approximately 2-3 hours and will include the following: Informed consent, Demographic data, Concomitant medications (no psychotropic medications will be allowed), Family history data, Medical evaluation including physical examination, EKG, weight, and vital signs, Urine pregnancy test (for women of childbearing years) and urine drug screen, and a psychiatric evaluation (using the following measures: MINI International Neuropsychiatric Interview (Sheehan et al., 1998); Neurocognitive assessments of impulsivity; Depressive symptoms will be rated with the 24-item Hamilton Depression Rating Scale (HAM-D) (Hamilton, 1960); Anxiety symptoms will be assessed using the Hamilton Anxiety Rating Scale (HAM-A) (Hamilton, 1959); Psychosocial functioning will be evaluated using the patient-rated version of the

Sheehan Disability Scale (SDS) (Sheehan, 1983); Quality of Life Inventory (QOLI) (Frisch et al., 1993); Compulsivity will be assessed using the Cambridge Chicago Trait Scale (Cambridge CHI-T Scale) ([name] & Chamberlain, 2016), the Lie Acceptability Scale (Goosie, 2014), The Narcissistic Personality Inventory (Raskin & Terry, 1988), The Social Desirability Scale (Crowne & Marlowe, 1960), and the Columbia Suicide Severity Rating Scale (C-SSRS)). If subjects consent, a blood sample will be collected to check for diabetes by measuring blood glucose levels.

At baseline, binge eating will be assessed using the following: Binge eating diary, Clinical Global Impressions–Severity Scale, the Three-Factor Eating Questionnaire, Self-Reported Binge Eating Scale, and the Yale-Brown Obsessive Compulsive Scale modified for Binge Eating (YBOCS-BE). Baseline labs, as well as interim labs, may be ordered based on clinical and medical evaluation.

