A medication error is a preventable event that involves an identifiable patient and that leads to inappropriate medication use, which may result in patient harm. While overdoses and underdoses constitute medication errors, doses missed inadvertently by a patient do not. Individuals who identify a potential medication error situation should immediately contact Takeda (see below) and report the event.

Phone: [name] ([name])

E-mail: [contact]

[contact]

Product complaints and medication errors in and of themselves are not AEs. If a product complaint or medication error results in an SAE, an SAE form should be completed and sent to Takeda Pharmacovigilance.

Statistical Analysis:

Design/Randomization

The study is a double-blind, placebo-controlled study. Participants will be randomized (1:1) to receive vortioxetine or placebo by the University of Chicago Investigational pharmacy in block sizes of eight, using computer-generated randomization with no clinical information.

Efficacy Analysis

For statistical analysis, the full-analysis set will be defined as all participants who took at least 1 dose of the study drug and had at least 1 post-baseline primary efficacy assessment. The safety-analysis set will be defined as all randomized participants who took at least 1 dose of the study drug and completed at least 1 follow-up safety assessment.

We will compare the baseline characteristics of both groups using Fisher's exact test for categorical variables and the t test for continuous variables. We will calculate adherence to treatment, based on the number of capsules returned at each visit, as the number of capsules taken divided by the number of days in the study \times 100%.

Primary endpoint analysis

The primary outcome measure will be the change from baseline in frequency of binge eating episodes (binges/week), defined as the mean number of binges per week in 2-week intervals. If the visit interval is less than 2 weeks, the mean number of binges per week will be estimated based on the number of binge days in the interval since the last visit.

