Between group comparisons will use a mixed-effects model for repeated measures, including fixed factors for treatment and visit, the interaction of treatment and visit, a covariate of the log-transformation ([baseline number of BE days per week] + 1), and the interaction of the baseline covariate and visit using visit as a categorical variable. Mixed-effects models for repeated measures estimates differences from placebo in the change from baseline of the log-transformed scale ([BE days per week] + 1) at week 12 (primary end point). Based on previous research, log-transformation should reduce skewness (McElroy et al., 2007).

Secondary endpoints analyses

Secondary outcome measures will include the change from baseline in frequency of binge days (or mean days per week when the participant had one or more binges), weight, body mass index, global improvement, Three-Factor Eating Questionnaire, and Impact of Weight on Quality of Life.

We will also analyze changes from baseline in log-transformed BE episodes, TFEQ factor scores, and YBOCS-BE total score to week 12 using the mixed-effects model for repeated measures. Pairwise χ^2 statistical tests will evaluate dichotomized CGI-I ratings at week 12 for placebo vs treatment group.

Response categories will be tabulated based on the percentage decrease in frequency of binges from baseline to endpoint, which will be defined as follows: complete=cessation of binges; marked=75% to <100% decrease; moderate=50% to <75% decrease; and none=<50% decrease.

We will calculate effect sizes for the primary analysis of binges per week and weight using Cohen's d. Finally, we will perform a Spearman rank correlation to assess the association between the change in frequency of binges from baseline to week 12 and the change in weight from baseline using completers.

Safety analyses

Adverse events will be collected at baseline visit. We will evaluate differences between groups in the incidence of treatment-emergent adverse events using Fisher's exact test. Descriptive statistics will be used to evaluate changes in laboratory values, blood pressure and heart rate.

Sample Size

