The sample size was calculated for the primary endpoint of change from baseline in binge eating days per week. For 80% power to compare the change from baseline in binge eating days per week on the log-transformed scale, assuming an effect size of 0.6 to 0.7 between treatment group and the placebo group, 40 participants will be needed in each treatment group based on a 2-group t test at the .05 level of significance. Given the particularly low rates of adverse events reported with Vortioxetine, as well as its more positive side effect profile in terms of sexual side effects compared to other antidepressants used in binge eating disorder, we expect few drop-outs from the study and therefore a smaller sample is needed.

Feasibility

Given our past experience and the pacing of the study, we feel the goal to enroll 80 subjects in 20 months is practical and attainable. Given no-shows and rescheduling, and the time required for recruitment, telephone and in-person screening, and related issues inherent in any human study, the current goal of averaging at least 4 subjects per month is reasonable based on the fairly high prevalence of binge eating disorder, the number of subjects calling our outpatient clinic, and the large recruitment area of metropolitan Chicago. We will also employ our standard participant friendly provisions, including scheduling sessions in late afternoon/early evening and weekends, incorporating technological advances for contacts and reminders, and providing adequate compensation for participants' time.

Data Management Plan:

Data collected will consist of demographic data, subjective (self-report questionnaires, interview responses, ratings), and physiological (weight, heart rate and blood pressure). Access to individually identifiable private information about human subjects will be limited to Drs. [name] and [name] and their staff and will be collected specifically for the proposed research project. All collected data will be stored utilizing a 4-digit subject identification code, linked to separately stored identifying information via a coded log

only available to the PIs.

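### The mixed model reused for the TFEQ, YBOCS-BE and binge-episode outcomes names only baseline binge days as a covariate; read literally, the scale-score comparisons lose precision

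*Combined protocol and SAP*

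**What the plan says.** Under Primary endpoint analysis (Statistical Analysis), between-group comparisons use a mixed-effects model with treatment, visit and treatment by visit. Its baseline terms are "a covariate of the log-transformation ([baseline number of BE days per week] + 1), and the interaction of the baseline covariate and visit". No other baseline term appears anywhere in the plan.

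Under Secondary endpoints analyses, the text continues: "We will also analyze changes from baseline in log-transformed BE episodes", followed by "TFEQ factor scores, and YBOCS-BE total score to week 12 using the mixed-effects model for repeated measures". The covariates are neither restated nor changed for these outcomes.

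The own baselines will be available. Baseline Visit Assessments says "At baseline, binge eating will be assessed using the following: Binge eating diary", and the same list includes "the Three-Factor Eating Questionnaire, Self-Reported Binge Eating Scale, and the Yale-Brown Obsessive Compulsive Scale modified for Binge Eating (YBOCS-BE".

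Under Design/Randomization, allocation is 1:1 "in block sizes of eight, using computer-generated randomization with no clinical information", so no baseline score is balanced by design.

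**The concern.** The secondary text refers back to the one model that has been defined. Taken at its word, change in YBOCS-BE or in a TFEQ factor is adjusted for baseline binge-day count and not for its own starting value. Baseline binge days may be only weakly related to a questionnaire score, in which case this is close to an unadjusted change-score analysis.

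Subtracting baseline does not replace adjusting for it. With equal SDs and a baseline to week-12 correlation rho below 1, the best slope on baseline is rho, whereas subtraction imposes a slope of 1. The excess, 1 - rho, adds noise to every estimate.

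At stake is precision on continuous secondary outcomes in a pilot of 80, and reproducibility: two analysts could fit different covariates and both claim to have followed the plan.

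**Working it through.** **1. The plan's own figure.** Sample Size gives 40 per arm for 80% power at a standardised effect of 0.6 to 0.7, alpha 0.05 (two-sided assumed). With n = 2 × (1.960 + 0.842)² / d², n is 44 at d = 0.6, 38 at 0.65 and 33 at 0.7 (45, 39 and 34 by the t test). The stated 40 lies within this range and corresponds to d of about 0.63. The figure concerns the primary endpoint only, so nothing below alters it.

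**2. Set-up for the secondary outcomes.** Take one follow-up time (week 12), equal SDs set to 1, and no dropout. Let rho be the outcome's baseline to week-12 correlation, and r the correlation of its baseline with baseline binge days. Assume that binge days relate to week 12 only through the outcome's own baseline. The documents give neither rho nor r, so both are assumed over a range.

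- Residual variance of change, given binge days: (1 - rho)²(1 - r²) + (1 - rho²)
- Residual variance of change, given own baseline: 1 - rho²
- Ratio: 1 + (1 - rho)(1 - r²)/(1 + rho)

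Example, rho = 0.5 and r = 0: 1 + 0.5/1.5 = 1.333, and √1.333 = 1.155.

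**3. Scale scores (r = 0 to 0.5).** The power column takes a comparison with 80% power under own-baseline adjustment and gives its power under the literal model, Φ(2.802/√ratio - 1.960).

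| rho | Variance ratio | SE larger by | Effective N of 80 | Power |
|---|---|---|---|---|
| 0.3 | 1.404 to 1.538 | 18.5% to 24.0% | 57 to 52 | 65.7% to 61.7% |
| 0.5 | 1.250 to 1.333 | 11.8% to 15.5% | 64 to 60 | 70.7% to 67.9% |
| 0.7 | 1.132 to 1.176 | 6.4% to 8.5% | 70.6 to 68 | 74.9% to 73.3% |

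A simulation of 20,000 trials at rho = 0.5, r = 0.3 gave a ratio of 1.30 (formula 1.303).

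**4. Binge episodes.** Baseline episodes should track baseline binge days closely. With r = 0.8 to 0.9, the SE is 5.0% to 9.3% larger at rho 0.3, 3.1% to 5.8% at 0.5 and 1.7% to 3.1% at 0.7.

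**5. Validity.** In the step 3 simulation, with no true effect, the mean estimate was 0.002 SD under the literal model and 0.001 SD with own baseline. A second simulation (4,000 trials, rho 0.5, r 0.4) gave type I error of 5.2% and 5.1%. The literal analysis is therefore unbiased over randomisation. In a single trial, the baseline difference between arms has an SE of √(2/40) = 0.224 SD. A one-SE imbalance, net of what binge days explain, moves the estimate by (1 - rho) × 0.224 × √(1 - r²). For r = 0 to 0.5 that is 0.157 to 0.136 SD at rho 0.3, 0.112 to 0.097 at 0.5, and 0.067 to 0.058 at 0.7. This is the same loss as in step 3, seen in one trial, and not an extra one.

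**6. Add own baseline, or swap it in?** Relax the assumption in step 2 and let s be the correlation of baseline binge days with the week-12 outcome. The variance of change given binge days is then 2(1 - rho) - (s - r)². Take the corner r = 0.4, s = 0:

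- rho 0.5: 1 - 0.16 = 0.84, against 0.75 with own baseline only. A swap lowers the SE by 5.5%.
- rho 0.7: 0.6 - 0.16 = 0.44, against 0.51. A swap raises the SE by 7.7%.

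With both covariates the residual variance is 1 - (rho² + s² - 2·rho·s·r)/(1 - r²). That is 0.702 at rho 0.5 (SE 8.6% lower than literal) and 0.417 at rho 0.7 (2.7% lower). The corner is unlikely in practice, but it shows why own baseline should be added for the scale scores.

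**The case against.** The covariate list stands under Primary endpoint analysis and serves a model for log(binge days + 1). There, the covariate is that outcome's own baseline. The secondary sentence names the method and does not say that the covariates are the same. An analyst could fairly carry over the form of the model and use each outcome's matching baseline. This objection stands to the extent that a reader might infer the plan has settled on omitting own baselines, and the text does not show that. It does not remove the point: the covariate is unstated, the only literal reading is the less precise one, and one sentence settles both.

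The outcomes are already changes from baseline and allocation is randomised, so a reader who infers bias or an invalid test goes too far. Step 5 shows neither. A reader might also infer an equal loss for all three outcomes; for episodes it is small.

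The secondary text omits the + 1 from the log of episodes, and a reader might infer that participants who stop bingeing would be lost from the analysis. The plan uses + 1 each time it defines the binge-day scale, so the omission reads as shorthand. Even taken literally, a zero would remove only that visit from a repeated-measures model, and the participant's non-zero visits would stay.

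Finally, this is a pilot powered only on its primary endpoint, which limits the weight of any secondary result.

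**Conclusion.** The point holds as a gap in specification whose literal reading costs precision on the TFEQ factor scores and YBOCS-BE total. The SE would be about 6% to 24% larger over rho 0.3 to 0.7 and r 0 to 0.5. For binge episodes the cost is about 2% to 9%.

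These sizes rest on assumed correlations, equal SDs, a single follow-up time, no dropout, and binge days acting only through the outcome's own baseline. If binge days carry independent information, the gain from own baseline alone can shrink or reverse, as step 6 shows, while using both covariates avoids that. Type I error, the primary analysis and the sample size are unaffected. It is worth correcting because the data are already to be collected.

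**What to change.** Add to Secondary endpoints analyses, for example: *Each secondary mixed model will also include the baseline value of the outcome analysed, on the same scale as that outcome, and its interaction with visit. For the TFEQ factor scores and YBOCS-BE total, the baseline binge-days term and its interaction with visit are kept. For episodes, analysed as log(BE episodes per week + 1), they may be dropped.* The binge-days term is largely redundant for episodes.

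The cost is a short addition to the text, made before unblinding. It needs no new data or participants. Each scale-score model gains one covariate with its visit interaction, that is, one parameter at each of the seven post-baseline efficacy visits (weeks 1, 2, 4, 6, 8, 10 and 12). At week 12 with no dropout, this takes roughly one error degree of freedom of 77 (80 less intercept, treatment and binge days).

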Secondary Aim/Objective: *(if applicable)*

A secondary aim of the study is to examine the effects of vortioxetine vs placebo on overall functioning and quality of life.

Primary Endpoint(s):

The primary efficacy measure is the number of binge eating days per week based on clinician interview and confirmation of identified Binge eating episodes in self-reported Binge eating diaries. The primary efficacy end point is the change from baseline to week 12 on the log-transformed scale (Binge eating days per week) + 1.

Secondary Endpoint(s): (if applicable)

Secondary efficacy measures include the number of Binge eating episodes per week, 1-week Binge eating episode response status, and 4-week cessation from Binge eating (free from Binge eating episodes). Other secondary endpoints include the change in weight/BMI between baseline and study endpoint, the Clinical Global Impressions–Improvement Scale (CGI-I) rated global improvement of symptoms over time (results will be dichotomized as improved [CGI-I ratings of 1 or 2 very much/much improved] or not improved [CGI-I ratings of 3-7]). The self-reported Eating Inventory, also known as the Three-Factor Eating Questionnaire, the self-reported Binge Eating Scale, the Yale-Brown Obsessive Compulsive Scale modified for Binge Eating (YBOCS-BE), the Quality of Life Inventory, the Hamilton Depression Rating Scale and the Hamilton Anxiety Rating Scale.

Study Plan:

Eighty individuals with binge eating disorder will be recruited for a double-blind, placebo-controlled pilot study in which Vortioxetine or placebo is administered in a 1:1 fashion. All 80 subjects will have binge eating disorder per DSM-5 criteria for at least a year. Following baseline measures, subjects will receive Vortioxetine (10mg for one week and then 20mg thereafter) or inactive placebo. Participants will be seen one week after the baseline visit (assessing the 10mg dose), one week after that (assessing the 20mg dose), and then every 2 weeks for the remainder of the 12-week period. At week 12, subjects will start a 1-week taper off the medication and will be seen at week 13. Efficacy and safety measures will be performed at each visit.

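### Weight and BMI change are declared secondary endpoints, but the plan gives them no model, test, interval or missing-data handling, and the one mixed model it defines adjusts for baseline binge days only

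*Combined protocol and SAP*

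**What the plan says.** The Secondary Endpoint(s) section states: "Other secondary endpoints include the change in weight/BMI between baseline and study endpoint". The Secondary endpoints analyses section repeats the declaration, listing changes from baseline that include "weight, body mass index, global improvement, Three-Factor Eating Questionnaire, and Impact of Weight on Quality of Life". Under Following-Up Visit Assessments, weight is recorded at every follow-up visit. By the visit schedule, that is weeks 1, 2, 4, 6, 8, 10 and 12 during treatment.

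The analyses are then assigned outcome by outcome:

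- The mixed model is extended to "changes from baseline in log-transformed BE episodes, TFEQ factor scores, and YBOCS-BE total score to week 12 using the mixed-effects model for repeated measures".
- The dichotomised CGI-I rating gets a chi-square test.
- Weight appears in two further places. One is the effect-size sentence, which promises "effect sizes for the primary analysis of binges per week and weight" by Cohen's d. The other is a Spearman correlation between change in binges and "the change in weight from baseline using completers".
- BMI does not appear again.

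The only mixed model written out is under Primary endpoint analysis. It has treatment, visit and their interaction, "a covariate of the log-transformation ([baseline number of BE days per week] + 1"), and the interaction of that covariate with visit.

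**The concern.** An endpoint that is declared and measured seven times on treatment should have a stated comparison between arms. Weight has only a standardised effect size whose construction is left open, and BMI has nothing. The choices that decide the answer (observed week-12 values, last available values or a model; which standard deviation; which covariate) would then be made after the data are seen.

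The Background ties the disorder to obesity, BMI and regain of lost weight, so readers will look for the weight result. A d without an interval does not tell them whether an effect on weight has been shown, excluded or left unresolved.

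The second part concerns outcomes that do have a model. The Three-Factor Eating Questionnaire and YBOCS-BE analyses refer back to the mixed model, and the only one defined carries a binge-day covariate. Read literally, those scores are adjusted for baseline binge days but not for their own baselines.

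**Working it through.** **1. The plan's own figure.** The Sample Size section gives 40 per arm for 80% power at an effect size of 0.6 to 0.7, with a two-group t test at 0.05. The two-sided normal approximation is n = 2(1.96 + 0.842)²/d² = 15.70/d². This gives 44, 38 and 33 per arm at d = 0.60, 0.65 and 0.70. The exact t test gives 45, 39 and 34. The stated 40 lies inside that range and corresponds to d of about 0.634. The figure concerns binge days. The documents give no power or precision figure for weight.

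**2. What is specified for each outcome.**

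| Outcome | Between-arm analysis | Interval or test named | Own baseline as covariate |
|---|---|---|---|
| Binge days (log) | Mixed model | Model-based difference at week 12 | Yes |
| Binge episodes (log) | Mixed model | Model only | No, binge days as written |
| TFEQ factors, YBOCS-BE | Mixed model | Model only | No, binge days as written |
| CGI-I (dichotomised) | Chi-square | Test | Not applicable |
| Weight | Cohen's d | None | Not stated |
| BMI | None | None | None |

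The Spearman correlation is not in the table because it relates two changes to each other and does not compare arms.

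**3. Precision of a bare d.** With n per arm, SE(d) = √(2/n + d²/(4n)). The inputs are n = 40 from the Sample Size section and illustrative values of d.

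- d = 0: SE = √(2/40) = 0.224, half-width 1.96 × 0.224 = 0.44.
- d = 0.2: SE = √(0.05 + 0.04/160) = 0.224, interval −0.24 to 0.64.
- d = 0.3: SE = √(0.05 + 0.09/160) = 0.225, interval −0.14 to 0.74.
- d = 0.5: SE = √(0.05 + 0.25/160) = 0.227, interval 0.05 to 0.95.

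If 32 per arm contributed (20% loss, assumed), the half-width at d = 0 would be 1.96 × √(2/32) = 0.49.

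**4. What an own-baseline covariate adds for weight.** With equal variances at baseline and week 12 and correlation r between them, adjustment for own baseline leaves (1 + r)/2 of the variance of a simple change-score comparison. The documents give no r. At assumed values of 0.90, 0.95 and 0.98 the ratio is 0.95, 0.975 and 0.99, a gain of 5%, 2.5% and 1%. For weight, then, the covariate itself adds little precision.

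**5. Drop-out.** The Sample Size section expects few drop-outs but gives no rate, so the documents do not allow a size to be put on any drop-out bias. What they do show is that up to seven on-treatment weights per participant are collected and that no rule says how a participant without a week-12 weight enters the weight comparison.

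**The case against.** The best defence is that the Primary endpoint analysis section says in general terms that between-group comparisons will use a mixed model, which could be taken to cover weight. That does not succeed. The sentence sits under the primary heading, its covariate and its estimated quantity are both binge days, and the later sentence beginning "We will also analyze changes from baseline in log-transformed BE episodes, TFEQ factor scores, and YBOCS-BE total score to week 12" would be unnecessary if every outcome were already covered.

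A second defence is that any competent analyst would swap in the right baseline. That is likely, but the text does not say it.

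A third is that a two-group d with known group sizes can be converted to an approximate interval, as the working does. This is correct. The objection to a bare d is that the plan does not require the interval, not that one cannot be obtained.

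Some stronger readings are tempting and should be resisted:

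- **That d is unadjusted or ignores baseline.** The plan does not say how d is built, and the endpoint is itself a change from baseline.
- **That the weight comparison uses only participants still present at week 12.** Only the Spearman correlation is restricted to completers. The Efficacy Analysis section defines a full-analysis set needing one dose and one post-baseline primary assessment. The endpoint is worded as change to study endpoint. The Drugs, Dosages, and Regimens section gives participants who stop for intolerance a final-visit assessment. An analysis of last available values fits the text as well as a completer analysis does.

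It also stands that this is a secondary endpoint in a study that calls itself a pilot.

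**Conclusion.** The point holds as a gap in specification. Weight change has no stated model, test, interval or missing-data handling, and its only between-arm quantity is a Cohen's d of undefined construction. BMI change has no analysis. The mixed model as written would also carry a binge-day covariate, in place of the outcome's own baseline, into TFEQ and YBOCS-BE.

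The size that can be shown is the uncertainty the plan leaves unreported: about ±0.44 standard deviations at 40 per arm, and about ±0.49 if 32 per arm contributed. The precision gain from a baseline-weight covariate is small, about 1% to 5% of the variance at an assumed correlation of 0.98 to 0.90. The main gains for weight are a reported interval and use of all visits when some participants leave early. The second gain relies on missingness being explained by observed data. A reader might infer that the planned weight result is biased by drop-out. The documents do not support that, because they neither commit to a completer analysis nor give a drop-out rate.

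The primary analysis and sample size are unaffected. The change is worth making, but it does not put the trial's main conclusion at risk.

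**What to change.** Amend the Secondary endpoints analyses section as follows:

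1. Add weight and BMI to the outcomes analysed with the mixed-effects model for repeated measures, in the full-analysis set.
2. State that for each secondary outcome in that list, the outcome's own baseline value and its interaction with visit replace the binge-day covariate and its interaction.
3. Report the week-12 difference between arms with its 95% interval.
4. Define Cohen's d as that difference divided by a stated standard deviation, for example the pooled standard deviation of change, and report it with an interval.

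It would help to say as well how a weight taken at an early final visit is assigned to a scheduled visit.

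The cost is one or two sentences and a few more runs of a model already planned. No new data, visits or participants are needed. The downside is a few more reported secondary estimates.

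### The planned Spearman correlation of binge change with weight change has no term for treatment arm; if the arms are pooled, drug effects on both outcomes would add a small between-arm component.

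*Combined protocol and SAP*

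**What the plan says.** The last analysis listed under Secondary endpoints analyses reads: "we will perform a Spearman rank correlation to assess the association between the change in frequency of binges from baseline to week 12". The second variable and the analysis set are given as "the change in weight from baseline using completers". There is one correlation and one set of participants. Nothing is said about pooling, stratifying or adjusting for arm.

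The same section does handle treatment elsewhere. The mixed model for the primary endpoint has treatment and treatment-by-visit terms, and the dichotomized CGI-I is compared between placebo and active arms.

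Both variables in the correlation are also compared between arms. The secondary outcomes include "frequency of binge days (or mean days per week when the participant had one or more binges), weight, body mass index", and the plan adds: "We will calculate effect sizes for the primary analysis of binges per week and weight using Cohen's d". For binge eating days the Sample Size section gives a planned effect: "assuming an effect size of 0.6 to 0.7 between treatment group and the placebo group". No effect size is given anywhere for weight.

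**The concern.** Treatment can be a common cause of the two changes. If the drug lowers binge frequency and also lowers weight, treated participants tend to sit low on both axes and placebo participants high on both. A correlation across all completers then picks up the distance between the arm means as well as any tendency, among people on the same treatment, for those who binge less to lose more weight. If the drug moves the two outcomes in opposite directions, the between-arm part works against the within-arm part and weakens it.

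What is at stake is the meaning of this one figure. A reader would probably take a positive correlation to mean that participants who cut down on bingeing lost weight. A pooled coefficient cannot separate that from the drug having acted on each outcome by its own route.

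**Working it through.** **Inputs from the documents.** Allocation is 1:1 ("Participants will be randomized (1:1) to receive vortioxetine or placebo", Design/Randomization). There are 40 per arm, and the planned standardized effect on log binge eating days is 0.6 to 0.7 (Sample Size).

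**Assumptions.** The weight effect d2 is not in the documents and is varied from 0 to 0.65 SD. The binge effect d1 is set at the midpoint, 0.65, and carried over from log binge days to change in binge frequency. Outcomes are normal and tests are two-sided at 5%. All 40 per arm complete, except where stated.

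**Step 1: the plan's own figure.** The section states "40 participants will be needed in each treatment group based on a 2-group t test at the .05 level of significance". With n per arm = 2(1.96 + 0.8416)² / d² = 15.70 / d²:

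- d = 0.60 gives 43.6, so 44
- d = 0.65 gives 37.2, so 38
- d = 0.70 gives 32.04, so 33

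The t-test versions are 45, 39 and 34. Forty per arm gives 80% power at d = 0.634, inside the stated range. The figure reproduces, and 0.65 is a fair value for the planned binge effect. The documents give no figure for the correlation itself.

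**Step 2: correlation induced by pooling.** With equal arms and no within-arm correlation, the pooled correlation is

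r = (d1·d2/4) / √[(1 + d1²/4)(1 + d2²/4)].

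For d1 = 0.65, 1 + d1²/4 = 1.1056. Then:

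- d2 = 0: r = 0
- d2 = 0.2: 0.0325 / √(1.1056 × 1.01) = 0.0325 / 1.0567 = 0.031
- d2 = 0.4: 0.065 / √(1.1056 × 1.04) = 0.065 / 1.0723 = 0.061
- d2 = 0.65: 0.1056 / 1.1056 = 0.096

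**Step 3: simulation of Spearman's rho**, 40 per arm, zero within-arm association:

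| Weight effect (SD, assumed) | Mean pooled rho | Pooled test significant at 5% |
|---|---|---|
| 0 | 0.00 | about 5% |
| 0.2 | 0.03 | about 6% |
| 0.4 | 0.06 | about 8% |
| 0.65 | 0.09 | about 13% |

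A rank correlation adjusted for arm stays near 5% throughout.

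**Step 4: fewer completers.** The documents expect few drop-outs but give no rate. If 20% are lost (32 per arm, an assumption), the rate falls from 10.1% to 9.0% at d2 = 0.5 and from 14.1% to 12.4% at d2 = 0.7. The mean rho hardly changes.

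**Step 5: opposite directions.** Suppose the within-arm correlation is 0.30 and the weight effect is −0.4 SD. On the same formula with the within-arm term added, pooled r = (0.30 − 0.065) / 1.0723 = 0.22. In simulation the power to detect the association is 45% pooled and 73% adjusted. With no weight effect, pooled r = 0.30 / √1.1056 = 0.29, and power is 69% pooled and 73% adjusted.

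**The case against.** The strongest objection is that the plan never says the arms are pooled. That is right: pooling is inferred from one correlation in one set of completers with no arm term. What the text does establish is that the handling of arm is not specified.

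Second, the artefact needs an effect on weight, and none is assumed. This also stands. With no weight effect there is no false-positive inflation, so a reader who concluded outright that the result is confounded, or that the test fails to hold 5%, would go beyond the documents. The section also attaches no significance level, hypothesis or success rule to this correlation, and the .05 in Sample Size belongs to the primary comparison. A pooled Spearman test is valid for its own null of no association across all completers. The inflation shown here is relative to a null of no association within arms, which is the null that matters for the reading most people would give the result.

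Third, a reader might infer that a real association would be hidden altogether, or that pooling could manufacture a substantial one. Neither follows. In the opposing case the correlation drops from 0.30 to about 0.22, which is attenuation. At the planned binge effect of 0.6 to 0.7, even a weight effect of 1.0 SD induces a rho of only about 0.15. It would also be wrong to call this a contrast with association within participants: each completer contributes one pair of changes, so the distinction is between within-arm and across-arm association.

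Finally, if weight falls because bingeing falls, the pooled association is not wholly spurious. That is so, and it is a reason to show the within-arm correlations, where such a link should also appear. The planned Cohen's d values would tell a reader whether both outcomes shifted, but not how far the shifts contributed to the correlation.

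**Conclusion.** The point holds as a conditional, low-priority one. The plan gives no arm term for this correlation and on its natural reading pools the arms. Under that reading, drug effects on both outcomes mix a between-arm component into the coefficient.

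Over the assumed weight effects of 0 to 0.65 SD, the distortion runs from none to a rho of about 0.09, and the false-positive rate for within-arm association from about 5% to about 13%. Tied or zero-heavy binge counts would change these figures somewhat. The more useful argument for acting is that adjustment keeps the error rate near 5% in every case checked and gives power at least as good as pooling in both cases compared. It touches neither the primary analysis nor the sample size.

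**What to change.** Replace the single correlation with a partial Spearman correlation between change in binge frequency and change in weight, adjusted for treatment arm, and report the vortioxetine and placebo correlations separately beside it. State this in the SAP before unblinding, so that the handling of arm is not chosen after the data are seen. The cost is one line of text, minor programming and one degree of freedom. No extra data or participants are needed.
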